5.3. STORAGE AND HANDLING OF IMP

The Pharmacist and/or Investigator will be responsible for receipt, proper storage, and usage of study drug, as well as for the IMP distribution, collection of used and unused vials and final disposal of the remaining IMP.

The investigational product must be stored at -20 ± 5 °C at the investigational sites, in an appropriate locked room accessible only to the pharmacist, the Investigator, or a duly designated person.

A temperature probe and data logger will accompany the drug on shipment. It is essential that the investigational sites will verify the temperature excursion during shipment vs. the acceptable storage conditions, in order to identify potential stability concerns during shipment. These must be immediately communicated to the Sponsor that will decide upon appropriate actions to be taken. The IMP will be stored in a locked place, sheltered from light. The vials will be not shaken since agitation of vials may cause foaming and/or particle formation.

On Day 1 (baseline visit), the study personnel will give to the patient the monthly boxes containing the study medications

Patient should bring the study medication, one monthly box, at home as soon as possible and immediately store it in a freezer at -20 ± 5 °C.

The weekly box must be kept at 2-8°C for 7 days protected from light; the daily vial can be kept at room temperature, before the patient will use the single vial for each instillation (both eyes) as long as 12 hours are not exceeded. Agitation of vials may cause foaming and/or particle formation. Drug preparation and administration instructions will be provided separately to the site and to the patients.

Together with the IMP monthly box, the patient will also receive a separate administration kit of vial adapters (one per vial), pipettes (3 per vial) and disinfectant wipes (3 per vial); some spare samples could be provided to ensure product administration.

IMP ophthalmic solution instruction will be provided to patients.

Patients will use one vial to instill one drop in both eyes (**group 1**: cenegeerin TID; **group 2**: vehicle TID) three times a day (approximately every 6 hours), starting in the morning when they wake up, for a total duration of 4 weeks" .

The contents of each vial are for the daily administration to both eyes only. After the last administration the used vial should be returned to the original medication box and is not to be reused.

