6. STUDY PROCEDURE AND ASSESSMENTS

The first patient first visit (FPFV) is defined as the 1st visit performed at one of the clinical centers by the 1st screened patient. The last patient, last visit (LPLV) is defined as the last visit performed at one of the clinical centers by the last patient (i.e., the last visit foreseen by the study protocol), independently of whether the patient completed or withdrew from the study. The First Patient In (FPI) is defined as the first randomized patient at one of the clinical centers.

Patients will be evaluated according to the following scheme:

Interventional phase

- Screening visit (day -8),
- Baseline (day 1+2),
- Week 2 (day 14±2),
- Week 4 (day 28±2) or early exit

Follow up visits

- Week 8 (day 56±2)
- Week 12 (day 84±4)
- Week 16 (day 112±7)
- Week 24 (day 168±7)

The schedule of study procedures and assessments is tabulated by visit in the Schedule of Evaluations in § 2.0.

The descriptions of the procedures to be performed at each visit are provided below.

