Visit 2 Week 2	Day 14±2	
The following procedures will be performed (order below is mandatory):
 
 ➤ Ocular examination of both eyes to be performed by the physician investigator: 
 • Assessment by SANDE questionnaire • Assessment by IDEEL questionnaire • Assessment of best corrected distance visual acuity (BCDVA) • External Ocular Examination • Schirmer test I (without anesthesia) • Slit-lamp examination (SLE) to assess the Eyelid - Meibomian glands, Eyelid – Erythema, Eyelid - Edema Lashes, Conjunctiva Erythema, Lens, Iris, Anterior Chamber, Corneal Horizontal Diameter • TFBUT • Ocular surface staining (NEI score - corneal and conjunctival fluorescein staining) • ➤ Concomitant ocular and systemic medications ➤ Frequency of patient's artificial tear use during first 2 weeks of treatment (to be reported in eCRF) ➤ AE monitoring 
During the visit 2, week 2, the patient must bring the diary assigned during the previous visit. The PI or a delegate must check if patient has correctly completed the diary. If not, the site staff must retrain the patient.
 
At completion of the assessment the patient will be discharged and will be asked to return for the end of treatment visit on day 28±2 (Visit 3 week 4).
 
The Investigator will dispense to the patients the preservative free artificial tears (Blink® Tears or equivalent), provided by Sponsor, to be used only if strictly needed by the patient (the patient must follow the instruction in the product leaflet).

At home	Days 14 ±2 – 28 ± 2	
 ➤ Self-administration at home of the IMP, three times daily every 6 h for both eyes (diary) ➤ Recording any new or changes in concomitant medications (diary) ➤ Recording any unusual medical conditions - AE monitoring (diary) ➤ Recording possible use of preservative free artificial tears (diary). 
Data will be recorded by the patient on the patient's diary.

	Day	Procedures/Assessments

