4.1 Investigational drug and study treatment

Oxervate®, an ophthalmic solution containing cenegegermin 20 mcg/mL, which is a recombinant human Nerve Growth Factor (rhNGF); reference product is vehicle. Test and reference will be instilled in both eyes according to the following scheme:

- Group 1: one drop of cenegegermin 20 mcg/mL will be instilled in both eyes three times daily (every 6 hours, e.g. 7:00 am, 02:00 pm; 09:00 pm).
- Group 2: vehicle eye one drop will be instilled in both eyes three times daily (every 6 hours, e.g. 7:00 am, 02:00 pm; 09:00 pm).

The IMP will be provided in a monthly box containing 28 daily vials. Together with the IMP monthly box, patients will be provided with enough pipettes and adaptors for the administration of the IMP.

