4.2 Date of first and last administration of study drug

The date of first administration of study drug is defined as the date of first administration of IMP as per IMP Administration eCRF form (information transcribed from Patient Diary).

The date/time of last administration of study drug is defined as the Date of last treatment administration as per End of treatment eCRF form. This value has to be consistent with IMP Administration information recorded on the corresponding eCRF forms. In case of different dates, the latest will be used as treatment end.

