4.4 Visit Schedule and Visit Windows

Assessments and study visits will be performed as listed in Paragraph no. 2 (“Schedule of evaluations”) and in Paragraphs no. 6 (“Study Procedure and Assessments”) of the Study Protocol [1] containing additional details about scheduled visits and time windows.

Scheduled visits and time windows are:

- Screening (Day -8)
- Visit 1 - Baseline (Day 1 + 2 days)
- Visit 2 - Week 2 (Day 14 ± 2 days)
- Visit 3 - End of treatment Week 4 (Day 28 ± 2 days)
- Visit 4 - follow-up Week 8 (Day 56 ± 2 days)
- Visit 5 - follow-up Week 12 (Day 84 ± 4 days)
- Visit 6 - follow-up Week 16 (Day 112 ± 7 days)
- Visit 7 - follow-up Week 24 (Day 168 ± 7 days)

For efficacy and safety endpoints, data will be evaluated according to the Visit at which they have been collected.

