12.5 Partial date conventions

Table 6: Algorithm for Treatment Emergence of Adverse Events

AE START DATE	AE STOP DATE	RULE for TEAE definition	RULE for “Treatment”/“Follow-up” study period definition for TEAE summaries
Known	Known, Partial or Missing	If AE start date < IMP start date, then not TEAE If AE start date \geq IMP start date, then TEAE	In case of Treatment Discontinuation: If start date \geq Date of last IMP intake, then Follow-up study period for TEAE occurrence. Otherwise, Treatment study period for TEAE occurrence. In case of NO Treatment Discontinuation: If start date \geq Date of “Day 21” visit, then Follow-up study period for TEAE occurrence. Otherwise, Treatment study period for TEAE occurrence.
Partial, but known components show that it cannot be on or after IMP start date	Known, Partial or Missing	Not TEAE	Not applicable

AE START DATE	AE STOP DATE	RULE for TEAE definition	RULE for "Treatment"/"Follow-up" study period definition for TEAE summaries
Partial, could be on or after IMP start date	Known	If AE stop date < IMP start date, then not TEAE If AE stop date \geq IMP start date, then TEAE	If TEAE, then Treatment study period for TEAE occurrence.
	Partial	Impute stop date as latest possible date (i.e. last day of month if day unknown or 31st December if day and month are unknown), then: If AE stop date < IMP start date, then not TEAE If AE stop date \geq IMP start date, then TEAE	
	Missing	Assumed TEAE	
Missing	Known	If AE stop date < IMP start date, then not TEAE If AE stop date \geq IMP start date, then TEAE	If TEAE, then Treatment study period for TEAE occurrence.
	Partial	Impute AE stop date as latest possible date (i.e. last day of month if day unknown or 31st December if day and month are unknown), then: If AE stop date < IMP start date, then not TEAE If AE stop date \geq IMP start date, then TEAE	
	Missing	Assumed TEAE	

NOTE: Assignment to "Treatment" or "Follow-up" study period is applicable only for TEAEs.

Table 7: Algorithm for Prior/Concomitant medications

MEDICATION START DATE	MEDICATION STOP DATE	RULE for prior or concomitant categorization
Known	Known	
If medication stop date < date of first dose of IMP, assign as prior
 
If medication stop date \geq date of first dose of IMP, assign as concomitant

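### SAP Table 6 starts the follow-up period for TEAEs at a Day 21 visit that does not exist, although SAP 4.2 already defines the end of treatment

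*SAP*

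**What the plan says.** SAP 11.1 classes each TEAE as occurring on treatment or in follow-up and refers to Table 6 for the rule. For a known start date, Table 6 has two branches:

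- **Treatment discontinued:** follow-up if onset is on or after the date of last IMP intake.
- **Treatment not discontinued:** follow-up if onset is on or after the "Date of “Day 21” visit, then Follow-up study period for TEAE occurrence".

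TEAEs with a partial or missing start date go to the treatment period.

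The SAP visit list gives "Visit 3 - End of treatment Week 4 (Day 28 ± 2 days"), and protocol section 6 gives "Week 4 (day 28±2) or early exit". Between the Week 2 and Week 4 visits, protocol 6.2 has the patient continue "Self-administration at home of the IMP, three times daily every 6 h for both eyes (diary").

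On the end of treatment, SAP 4.2 states: "The date/time of last administration of study drug is defined as the Date of last treatment administration as per End of treatment eCRF form". Where the sources disagree, it adds: "In case of different dates, the latest will be used as treatment end".

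**The concern.** The branch for patients who did not discontinue depends on the date of a visit that no schedule contains, so it cannot be programmed as written. SAP 11.1 offers no other cut-off, and the list of changes from the protocol in SAP 7.9 does not mention one. Whoever programs the tables must choose a substitute, and plausible choices differ by about a week of on-drug time.

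The choice matters because protocol 9.4.5 requires TEAEs by study period. Timing is also a result the sponsor relies on: protocol 2.2 reports that adverse reactions in the Phase II study were confined to the treatment weeks. A comparison with that finding needs a sound split here. SAP 6.2 places the analyses after lock and unblinding, so an uncorrected rule could end up being settled with treatment codes known.

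The discontinuer branch has a smaller fault. It places an event that begins on the day of last dosing in follow-up, although the patient was dosed that day. An event that led to stopping on its day of onset would then appear in the follow-up column of Table 14.3.1.8.

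**Working it through.** The plan states no figure to reproduce. The check sets the schedule against Table 6 and then counts days.

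**1. Is Day 21 inside any visit window?** Windows from SAP 4.4, with the same schedule in protocol sections 2, 6 and 7.1:

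| Visit | Days |
|---|---|
| Baseline | 1–3 |
| Week 2 | 12–16 |
| Week 4 (end of treatment) | 26–30 |
| Week 8 | 54–58 |
| Week 12 | 80–88 |
| Week 16 | 105–119 |
| Week 24 | 161–175 |

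Day 21 is in none of them.

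**2. Are patients dosing on Day 21?** Yes. Treatment lasts 4 weeks (protocol 5.4.2). SAP 4.1 says "The IMP will be provided in a monthly box containing 28 daily vials", and protocol 5.3 says "The contents of each vial are for the daily administration to both eyes only". One vial a day gives dosing on Days 1–28.

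**3. On-drug days labelled follow-up, by substitute chosen:**

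- Study day 21, last dosing day counted as treatment: Days 21–28 = 28 − 21 + 1 = 8 days; 8/28 = 28.6%.
- Study day 21, compared with a Day 28 visit under the same on-or-after rule: that rule gives treatment days 1–27, of which Days 21–27 = 7 are lost; 7/27 = 25.9%. Over all 28 dosing days the same 7 days are 7/28 = 25.0%.
- Week 4 visit date: at most the visit day, because study boxes are returned at that visit (protocol 5.5).

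The study day 21 figures move with the actual end of treatment. Counting the end day as treatment, an end on Day 26 gives 6/26 = 23.1%. An end on Day 30 would give 10/30 = 33.3%, but 28 daily vials do not cover 30 days.

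**4. How does Table 6 compare with the rest of the SAP?**

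- SAP 4.2 takes last IMP administration as treatment end.
- Table 3 computes exposure as last minus first administration plus 1, so the last dosing day is a day of exposure.
- Table 3 assigns artificial-tear drops up to the End of Treatment date to treatment and later drops to follow-up.
- Table 6 follows none of these for patients who did not discontinue. For discontinuers it uses last intake but gives that day to follow-up, a discrepancy of one day per patient.

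**5. Which outputs are affected?** Of the ten TEAE tables 14.3.1.1 to 14.3.1.10 in SAP 15.1, six are split by period: .2, .3, .5, .6, .8 and .9. The Day 21 branch reaches five (.2, .3, .5, .6, .9), because .8 holds only patients who stopped IMP. The last-intake branch reaches all six.

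**The case against.** The existence of the error is hard to dispute; the case against concerns its weight and the remedy.

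- **Hypothetical size.** The percentages arise only if someone reads the rule as study day 21, and they assume treatment ends on Day 28. This is right, and they are presented on that basis. The 25.9% also drops Day 28 from the denominator; that follows from the on-or-after rule, and the alternative is 25.0%.
- **The discontinuer rule is workable.** It can be applied as written, and counting exposure days is a different task from assigning event onsets. This stands in part: it is a one-day boundary matter, secondary to the missing visit, and it reaches Table 14.3.1.8 only for onsets on exactly the last-intake day.
- **The SAP has more than one anchor.** Table 3 also uses the End of Treatment visit for scheduled drops, and its day counts for artificial tears include the End of Treatment date in both periods. So the documents do not force the choice of last administration. It is nevertheless the date SAP 4.2 calls treatment end and the one Table 6 already uses for discontinuers.
- **Limited consequence.** Only descriptive period columns change, and the Phase II sentence is background. That limits the severity but does not make the rule usable. The blind data review meeting before lock (SAP 7.10) might catch the error, but nothing in the text ensures it.

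**Conclusion.** The concern holds. For TEAEs with a known start date in patients who did not discontinue, the treatment/follow-up rule refers to a visit outside every schedule, at a time when patients are still dosing. As written it yields no split.

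With study day 21 substituted, about a quarter of on-drug days (25.9% to 28.6%, assuming dosing on Days 1–28) would be called follow-up; with the Week 4 visit substituted, at most one day. The documents give no onset rates, so these shares cannot be turned into numbers of events. For discontinuers the misplaced time is one day each.

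Overall TEAE counts, the overall columns, the four unsplit tables and the efficacy analyses are untouched. This should be corrected before database lock.

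**What to change.** In the Table 6 period cell for known start dates, replace both branches with one rule for all patients: **Treatment if the AE start date is on or before the date of last IMP administration (SAP 4.2); otherwise Follow-up.** This removes the nonexistent visit, agrees with the exposure formula in Table 3 and settles the boundary day.

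State a default for a patient with no recorded last-dose date on the End of treatment form, for example the latest dosing date on the IMP Administration forms, which SAP 4.2 already cross-checks.

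A secondary clarification can go in at the same time. The two Table 6 entries that class pre-dose onsets as not treatment-emergent should note that the worsening clause of SAP 11.1 prevails, with the period taken from the date of worsening where one is recorded. Protocol 8.3 does not list such a date among the AE items, so the note can apply only where it exists.

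The cost is one cell of one SAP table and a short note. The last-dose date is already collected, and no study procedure changes.

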5.4.2. Dose regimen

In all patients both eyes will be treated for a period of 4 weeks.

The dosing scheme of the different study groups is summarized below:

Group 1: one drop of cenegegermin 20 mcg/mL will be instilled in both eyes three times daily (every 6 hours, e.g. 7:00 am, 01:00 pm; 07:00 pm).

Group 2: one vehicle drop will be instilled in both eyes three times daily (every 6 hours, e.g. 7:00 am, 01:00 pm; 07:00 pm).

During the 4 weeks of masked treatment only the administration of IMP is allowed. Nevertheless, if strictly needed, the patient can take a preservative free artificial tears (provided by the Sponsor). The use (n° drops/day) of preservative free artificial tears will be clearly documented in a patient's diary and in the eCRF.

Both the patients and the investigator will be masked to the study treatment.

Information about the study drug administration, and comments, will be recorded on the appropriate page of the eCRF.

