8.3. RECORDING

AE data should be obtained through observation of the patient, from any information volunteered by the patient, and through patient questioning.

Adverse Events:

All AEs (non-serious and serious) that occur during the course of the study will be recorded in the eCRF. Any pre-existing medical conditions or signs/symptoms present in a patient prior to the start of the study (i.e., before informed consent is signed) should be specified in the dedicated eCRF sections. Subsequent to signing an informed consent form, all untoward medical occurrences that occur during the course of the study must be documented on eCRF. AEs will be collected till last Follow Up visit (week 24).

When possible, signs and symptoms indicating a common underlying pathology should be documented as one comprehensive event. For each recorded event, the AE documentation must include the onset date, outcome, resolution date (if event is resolved), intensity (i.e., severity), any action with study treatment taken as a result of the event, and an assessment of the adverse event relationship to the study treatment.

Serious Adverse Events:

The Investigator must record all SAEs, including sight-threatening events, occurring at any time during the study (after signature of the informed consent) regardless of presumed causal relationship, on the Serious Adverse Event form in the eCRF of the EDC system within 24 hours of learning of the event; information on the SAE must also be recorded on a specific Non-Carbon Repeat SAE form (included in the Investigator's Site File).

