11.1 Adverse events

Adverse Events (AEs) started before administration of study treatment will be considered as pre-treatment; any AE started on or after the date of the first dose of study medication or started prior to first dose and worsened in severity after the first dose will be considered as Treatment-Emergent Adverse Event (TEAE).

In case of missing or incomplete dates not allowing a direct allocation to any of the two categories of AEs (pre-treatment/TEAE), an allocation will be done according to the available parts of the onset and the end dates (see Table 6). In case of TEAE, the event can be further classified as:

- On Treatment period, or
- On Follow-up period

according to the available parts of the onset and the end dates (see Table 6).

All AEs will be coded by SOC and PT according to MedDRA thesaurus. In addition, each AE will be graded to capture the relationship to IMP and severity (see protocol for details).

Pre-treatment AEs will be presented in the listings only.

TEAE summaries will be presented, displaying frequencies and percentages of patients reporting AEs within each SOC in decreasing order of total frequency. Along with AEs, number of events will be reported. On each of these summaries, patients will be counted only once per SOC and, within each SOC, patients will be counted only once per PT.

“Possible”, “Probable” and “Highly Probable” or missing relationships will be considered as related to study drug (ADR – Adverse Drug Reaction) for the summary tables. “None” and “unlikely” relationships will be considered not related to study drug.

The following table will be presented by treatment group and overall:

- A summary overview (patient with at least one event, percentage, and number of events) of:
 - TEAEs,
 - Ophthalmic TEAEs,
 - Non-Ophthalmic TEAEs,
 - severe TEAEs,
 - severe Ophthalmic TEAEs,
 - severe Non-Ophthalmic TEAEs,
 - serious TEAEs,
 - serious Ophthalmic TEAEs,
 - serious Non-Ophthalmic TEAEs,
 - non-serious TEAEs,
 - ADRs,
 - Ophthalmic ADRs,
 - Non-Ophthalmic ADRs,
 - serious ADRs,
 - TEAEs leading to discontinuation of IMP,
 - TEAEs leading to discontinuation of study,
 - TEAEs leading to death.

The following tables will be presented by treatment group:

- Summary of Ophthalmic TEAEs by primary SOC and PT and by study period (on treatment/follow-up and overall).
- Summary of Non-Ophthalmic TEAEs by primary SOC and PT and by study period (on treatment/follow-up and overall).

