- Summary of TEAEs by primary SOC, PT and Severity.
- Summary of Serious TEAEs by Primary SOC and PT and by study period (on treatment/follow-up and overall).
- Summary of ADRs by Primary SOC and PT and by study period (on treatment/follow-up and overall).
- Summary of ADRs by Primary SOC and PT and Severity.
- Summary of TEAEs leading to IMP Discontinuation by Primary SOC and PT and by study period (on treatment/follow-up and overall).
- Summary of TEAEs leading to study Discontinuation by Primary SOC and PT and by study period (on treatment/follow-up and overall).
- Summary of TEAEs leading to Death by Primary SOC and PT.
- Listing of Deaths.

12. Derivations and date conventions

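### SAP Table 6 puts a TEAE with a partial start date in the Treatment period even when its known month or year lies wholly after treatment ended

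*SAP*

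**What the plan says.** SAP section 11.1 classifies each TEAE as occurring in the treatment or the follow-up period "according to the available parts of the onset and the end dates (see Table 6").

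Table 6 in SAP section 12.5 then gives the rules by type of start date:

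- **Fully known start.** The start is compared with an end-of-treatment cut-off, and an onset on or after it is Follow-up. The cut-off is the last IMP intake for patients who discontinued treatment, and the date of a Day 21 visit for everyone else.
- **Partial start that must precede first dose** ("Partial, but known components show that it cannot be on or after IMP start date"). Not a TEAE.
- **Partial start otherwise** ("Partial, could be on or after IMP start date"). TEAE status may depend on the stop date. The period cell says only "If TEAE, then Treatment study period for TEAE occurrence".
- **Missing start.** The same single period rule.

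Protocol section 5.4.2 sets the length of treatment: "In all patients both eyes will be treated for a period of 4 weeks". Protocol section 8.3 sets the length of AE collection: "AEs will be collected till last Follow Up visit (week 24"). The SAP's by-period outputs include "Summary of ADRs by Primary SOC and PT and by study period (on treatment/follow-up and overall").

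**The concern.** The table uses the known month and year at the start of treatment, where they can show that an event is not treatment-emergent. It has no matching step at the end of treatment. Nothing in the partial-start row can produce Follow-up, however late the recorded month. That departs from the principle in section 11.1 and from the table's own treatment of full dates: two events in the same month can land in different periods only because one lacks a day.

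At stake is the treatment/follow-up split in six tables: ophthalmic TEAEs, non-ophthalmic TEAEs, serious TEAEs, ADRs, TEAEs leading to IMP discontinuation and TEAEs leading to study discontinuation (Tables 14.3.1.2, 14.3.1.3, 14.3.1.5, 14.3.1.6, 14.3.1.8 and 14.3.1.9). Listings print partial dates with dashes for the missing part, so an AE listing could show a month that visibly disagrees with the period table.

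**Working it through.** The plan states no figure on this point, so there is none to reproduce. The check applies Table 6 as a decision rule.

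**Worked example.** Take a first dose on 01MAR2022. With 28 days of treatment the last dose is 28MAR2022, and day 168 is 15AUG2022.

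| Recorded start | Earliest possible onset | Could it be on treatment? | Table 6 |
|---|---|---|---|
| --MAR2022 | 01MAR2022 | Yes | Treatment |
| --APR2022 | 01APR2022 | No | Treatment |
| --JUN2022 | 01JUN2022, 65 days after last dose | No | Treatment |
| 15JUN2022 | 15JUN2022 | No | Follow-up |

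May, July and August behave like April and June. The last row is Follow-up for a discontinuer by the last-intake rule. For a completer it is Follow-up whether the Day 21 visit is read as the day 14 or the day 28 visit.

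The stop date cannot rescue the rule. It bounds onset only from above, so it can confirm Treatment but never show Follow-up. The missing step is a comparison of the earliest possible start with the cut-off.

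**How much of the follow-up onset is identifiable.** Inputs: 28 days of treatment, collection to day 168. Assumptions: first doses spread evenly over a year, onset uniform from the day after last dose to day 168, and an event counted as identifiable if the first day of its known month (or year) is after the last dose.

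- Only the day missing: 89.6%, 89.5% and 89.3% of follow-up onsets are identifiable for a last dose on day 26, 28 and 30.
- Hand check: about 15 days remain in the month containing day 28, so (140 − 15)/140 = 125/140 = 0.893.
- Only the year known: about 19%.
- Table 6 as written places 0% of these in Follow-up.

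**As a share of all TEAEs with only the day missing.** If a fraction f of them begin in follow-up, the misplaced share is about f × 0.893.

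- Uniform onset over 168 days: f = 140/168 = 0.833, giving 125/168 = 0.74.
- Half in follow-up: 0.5 × 0.893 = 0.45.
- None in follow-up: 0.

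The multiplier 0.893 itself assumes even onset within follow-up. If onsets cluster just after treatment, more of them share a calendar month with the last dose and the share falls.

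**The case against.** The strongest case is that the rule may never matter in practice. Protocol section 8.3 requires an onset date for every AE. Patients keep a diary through week 24, which is reviewed at visits, and section 8.2 has AEs asked about at each visit. Edit checks, queries and a blind data review come before lock. Partial onsets arising in follow-up should therefore be few. This stands as a limit on size. It does not justify the rule, since the row exists precisely for the dates that remain incomplete.

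Defaulting to Treatment is also a familiar cautious convention and applies equally to both arms. For ambiguous or missing dates that is a sound choice and should stay. It does not cover dates whose known part already excludes the treatment period.

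Section 11.1 defers to Table 6 and does not set a rival rule. That is fair: the conflict is between a stated principle and its execution.

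A reader might go further and infer that about three quarters of partially dated events will be misplaced, or that the trial will misstate when reactions occur. The documents do not support either. The 74% is a share of an unknown count under assumed uniform onset. For adverse reactions, Protocol section 2.2 reports that in the 261-patient Phase II dry eye study they occurred only during the 4 weeks of treatment. If that pattern repeats, the misplaced share of ADRs would be near zero.

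**Conclusion.** The point holds as a minor error in a stated rule. Table 6 sends every TEAE with a partial start date that could be on or after first dose to Treatment, including those whose known month or year rules that out. This conflicts with SAP section 11.1 and with the table's handling of full dates.

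The effect is confined to the treatment/follow-up columns of the six by-period tables. Those tables also carry an overall presentation, which does not change; nor do TEAE status, the overview, severity and death tables, or any efficacy result. The number of events affected is unknown and probably small. The percentages above rest on the stated onset assumptions and are illustrative only. Wholly missing start dates are outside the point, because they carry no onset information.

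**What to change.** In the partial-start row of Table 6, derive the earliest possible start from the known components (the first of the known month, or 1 January of the known year). If that date shows that onset cannot precede the end-of-treatment cut-off, assign Follow-up; otherwise keep Treatment. Leave the missing-start row as it is.

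Use the same cut-off, with the same on-or-after convention, as the known-date row, so that partial and full dates follow one boundary. A separate wording such as after the last IMP date would add a third boundary. The known-date row needs attention first: for patients who did not discontinue it refers to a Day 21 visit, while SAP section 4.4 and the protocol schedule list visits at day 14 and day 28 and none at day 21. The sponsor should reconcile these passages and state one cut-off.

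The cost is one line in the SAP table and the matching line in the derivation program, plus that reconciliation, all made before unblinding. No new data are needed.
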